#### 9.4.2 ANALYSIS OF THE PRIMARY EFFICACY ENDPOINT(S)

All primary endpoints will be measured as continuous variables and will be repeated after each intervention performed on a given study visit. A one-way ANCOVA will be used to assess treatment effects. Covariates will include basic cardiovascular and haemodynamic variables that may confound primary endpoints. These covariates include heart rate, blood pressure, and pulse wave velocity. Results will be presented as adjusted means with standard deviations. Primary endpoints will only be analyzed for participants who complete the entirety of at least one phase of the proposed study. Missing data will be imputed using mean imputation from all other measurements collected from the given participant. Outliers will be included and excluded in independent analysis, both of which will be reported.

---

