## 4 STUDY DESIGN

### 4.1 OVERALL DESIGN

The study will use a randomized cross-over design. It will be structured by division into two phases. Both phases will examine the acute cardiovascular response to cannabis consumption,

both at rest and during exercise. *Phase I* will examine if and how this response differs whether cannabis is smoked or vaporized. *Phase II* will examine how this response is influenced by cannabinoid concentration within inhaled cannabis. Phase II of the current study will use a single-blind design, with participants being unaware of the relative cannabinoid concentrations of the cannabis they consume. Cannabis will be inhaled using methods of smoking (phase I only) or vaporization (phase I and II). Each experimental study visit (study visits 2-9), 100mg of cannabis will be consumed via one of the two aforementioned methods of inhalation, followed by a subsequent rest period, or by 20 minutes of exercise. Primary endpoints will be examined pre- and post-consumption each visit (with the exception of muscle sympathetic nerve activity, which will only be performed on a single study visit), while secondary endpoints will be recorded during exercise.

Each phase of the study will require participants to complete an introductory and control visit, as well as 4 experimental study visits, where cannabis inhaled under alternating conditions (phase I: smoking vs. vaporizing high THC cannabis, phase II: high CBD cannabis vs. high THC cannabis) followed by exercise, or a time-matched rest period. The order in which these visits will occur will be randomized, and individualized for each participant. A within-subjects design will be utilized, so that each participant completes each condition. High THC cannabis used will be the cannabis strain “Rex”, while the high CBD strain will be “Kalea”. The dose size and strength will not be altered throughout the course of the study.

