## 4.2 SCIENTIFIC RATIONALE FOR STUDY DESIGN

A within subject design has been chosen for this study due to potential variability in primary endpoints between individuals. Specifically, variation in pulse wave velocity and flow-mediated dilation. Published reference values for pulse wave velocity in our selected age group may range between 3.92m/s and 8.26m/s. This substantial range requires a within-subjects design to allow for meaningful assessment of the effects of cannabis on arterial stiffness. Similar to pulse wave velocity, flow-mediated dilation may vary substantially between and within subjects, with values as high as 20% reported in healthy individuals. This design is further warranted due to the choice of secondary endpoints. Exercise performance, and the accompanying physiological responses, are highly dependent on numerous factors that are likely to vary between individuals. Such factors include weight, fitness level, and familiarity with cycling. This further warrants the need for a within subject design, as these variables would have to be

matched if using parallel groups. Even if groups were matched, there is a strong likelihood that significant variability would exist in performance metrics.

The proposed study does not employ a placebo-control or a double-blind design. This is a consequence of the challenge owed to masking the device used to inhale cannabis in phase I. Vaporization and smoking are distinct methods of cannabis inhalation, and as such different devices must be used, making blinding difficult. A single-blind design will be utilized in phase II, in that participants will not be aware of the strain of cannabis they are consuming. Although collection will not be double-blind, investigators will be blind to condition during data analysis.

Randomization of the order of experimental visits in each phase will occur to combat improvement in performance as a result of better of pacing strategies, or improvements in fitness. Randomization will be performed using a randomization software ([www.random.org](http://www.random.org)). The order in which visits will occur will be individualized to each participant.

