## 9.2 SAMPLE SIZE DETERMINATION

In accordance with our power calculation, 15 participants are required to have a power of at least 0.8 with an alpha of 0.05, for expected changes in measures of endothelial function (pilot work, change in FMD in response to exercise pre =  $4.8 \pm 2.5$  %, post =  $2.7 \pm 1.7$ %) (FMD in rats in response to cannabis smoke, pre =  $7.5 \pm 2.5$ %, post =  $2.4 \pm 1.4$  %), artery stiffness (pilot work, change in PWV pre =  $7.4 \pm 1.3$  m/s, post (at rest) =  $6.0 \pm 1.3$  m/s) and cardiac function (pilot work, peak longitudinal strain: pre =  $-18.3 \pm 1.2$  %, post =  $-17.0 \pm 1.9$  %), therefore we will recruit 20 participants in each phase of the study to account for potential dropout.

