## 9.4 STATISTICAL ANALYSES

### 9.4.1 GENERAL APPROACH

Our study will be divided into two phases each of which will be analyzed independently. All tests of significance will be two-tailed, and statistical significance will be based upon an alpha error probability of 5% and a power for 80%. The data will be evaluated using both parametric and non-parametric tests, as applicable. If the data are found to be not normally distributed, the raw data will be transformed using an appropriate transformation model in order to perform the parametric assessments. Non-parametric tests will be performed on raw data. The data will be assessed as continuous and will be presented as means with standard deviations. A one-way analysis of covariance will be used to assess the treatment

effects (Phase I: exercise, vaporizing THC, smoking THC, vaporizing + exercise THC, smoking THC + Exercise, Phase II: exercise, vaporizing THC, vaporizing CBD, vaporizing + exercise THC, Vaporizing CBD + Exercise) on the primary endpoints. Covariates will be introduced into the models in order to assess the impact of certain potential factors on outcome, including fitness, blood pressure, resting heart rate, and any other factors that are observed during the study that appear to potentially influence the outcome.

Our secondary endpoints will be assessed using a repeated measures one-way ANOVA and paired t-tests. If there are significant interactions differences between pairs of means will be determined with a Bonferroni post-hoc test.

---

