### 4. STATISTICAL ANALYSES

#### 1. GENERAL APPROACH

Our study will be divided into two phases each of which will be analyzed independently. All tests of significance will be two-tailed, and statistical significance will be based upon an alpha error probability of 5% and a power for 80%. The data will be evaluated using both parametric and non-parametric tests, as applicable. If the data are found to be not normally distributed, the raw data will be transformed using an appropriate transformation model in order to perform the parametric assessments. Non-parametric tests will be performed on raw data. The data will be assessed as continuous and will be presented as means with standard deviations. A one-way analysis of covariance will be used to assess the treatment effects (Phase I: exercise, vaporizing THC, smoking THC, vaporizing + exercise THC, smoking THC + Exercise, Phase II: exercise, vaporizing THC, vaporizing CBD, vaporizing + exercise THC, Vaporizing CBD + Exercise) on the primary endpoints. Covariates will be introduced into the models in order to assess the impact of certain potential factors on outcome, including fitness, blood pressure, resting heart rate, and any other factors that are observed during the study that appear to potentially influence the outcome.

Our secondary endpoints will be assessed using a repeated measures one-way ANOVA and paired t-tests. If there are significant interactions differences between pairs of means will be determined with a Bonferroni post-hoc test.

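### The primary endpoints other than MSNA are analysed with a one-way ANCOVA that names no participant term, so a five-condition crossover is tested against the wrong error term

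*Protocol*

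**What the plan says.** - **Design.** Protocol section 4.1: "A within-subjects design will be utilized, so that each participant completes each condition". Section 4.2 gives the reason: "A within subject design has been chosen for this study due to potential variability in primary endpoints between individuals".
- **Primary analysis.** Protocol section 9.4.2: "A one-way ANCOVA will be used to assess treatment effects". The SAP's general approach agrees: "A one-way analysis of covariance will be used to assess the treatment effects". Each phase has five levels: exercise alone, two cannabis conditions at rest, and the same two with exercise.
- **Covariates.** Section 9.4.2: "These covariates include heart rate, blood pressure, and pulse wave velocity". It does not say when in the visit they are taken. Section 9.4.1 specifies resting values for heart rate only, and adds covariates to "assess the impact of certain potential factors on outcome, including fitness" and other factors.
- **Secondary analysis.** Section 9.4.1: "Our secondary endpoints will be assessed using a repeated measures one-way ANOVA and paired t-tests".
- **Sample size.** Section 9.2: "15 participants are required to have a power of at least 0.8 with an alpha of 0.05". Neither the test nor the within-person correlation is stated. Twenty per phase are recruited, and section 7.2 replaces participants who discontinue.
- **MSNA.** It is recorded at a single visit, so it has no between-condition contrast and lies outside this point.

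**The concern.** The design is meant to remove between-person differences from the comparison of conditions. A one-way model treats the five values from one person as if they came from five people, so those differences go back into the error term. Three things follow.

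1. Standard errors of condition contrasts are wrong, and the stated 5% level and 80% power do not describe the tests that will be run.
2. A person-level covariate such as fitness is counted as five independent observations per person, so its own standard error is too small.
3. A covariate that varies both between people and between visits gets one pooled slope. If the covariate itself responds to cannabis, that slope can move the adjusted condition means when there is no effect.

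Section 9.1 also predicts no effect in several cells, such as CBD on pulse wave velocity (PWV). An insensitive test could make such predictions look confirmed.

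**Working it through.** **Step 1: the plan's own figure.** Inputs from section 9.2 for strain: change 1.3, SDs 1.2 and 1.9. Paired t-test, two-sided 5%, noncentral t:

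SD of difference = √(1.2² + 1.9² − 2r·1.2·1.9).

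At r = 0.5 this is √(5.05 − 2.28) = 1.664, and 1.3/1.664 = 0.781. Power at n = 15 is 0.803, so 15 is reproduced. At r = 0.4 strain needs 18, and at r = 0.6 it needs 13. At r = 0.5 flow-mediated dilation (FMD) needs 11 and PWV 9, so strain sets the size. Two independent samples would need 25 per condition for strain. The stated 15 therefore fits a paired analysis with r near 0.5, not a one-way model.

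**Step 2: direction.** With equal correlation r and variance σ², the difference of two condition means has variance 2σ²(1 − r)/n. The one-way model estimates it as 2σ²/n. The standard error is overstated by 1/√(1 − r): 1.05, 1.20, 1.41 and 1.83 at r = 0.1, 0.3, 0.5 and 0.7.

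**Step 3: size, by simulation.** Assumptions: five conditions, complete data, post-consumption values, no covariates, pilot changes standing in for condition contrasts. Pooled strain SD = √((1.2² + 1.9²)/2) = 1.589. Error degrees of freedom are 5(n − 1) one-way and 4(n − 1) with participant. For n = 15:

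| r | Omnibus type I, one-way | Contrast type I, one-way | Strain contrast power, one-way | Same, with participant |
|---|---|---|---|---|
| 0.1 | 3.4% | 3.9% | 0.60 | 0.64 |
| 0.3 | 1.2% | 2.1% | 0.62 | 0.75 |
| 0.5 | 0.2% | 0.8% | 0.64 | 0.87 |
| 0.7 | 0.01% | 0.1% | 0.67 | 0.98 |

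With the participant term, type I error stays at about 5% throughout.

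Strain at r = 0.5, one-way against participant term:

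- Phase I omnibus (all four cannabis conditions shifted by 1.3, exercise control not): 0.48 vs 0.88 at n = 15; 0.69 vs 0.97 at n = 20.
- Phase II omnibus (only the two THC conditions shifted): 0.76 vs 0.98 at n = 15; 0.92 vs 0.997 at n = 20.
- Single contrast at n = 20: 0.80 vs 0.95.

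Other endpoints, one-way contrast, n = 15: FMD (change 2.1, pooled SD 2.138) 0.795 at r = 0.3 and 0.83 at r = 0.5; PWV (1.4, SD 1.3) 0.90 at r = 0.5.

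**Step 4: what covariates recover.** Strain contrast, one-way, r = 0.5. If a person-level covariate absorbs 25, 50 or 75% of between-person variance, power is 0.71, 0.77, 0.83 at n = 15 and 0.85, 0.89, 0.93 at n = 20. The Phase I omnibus at n = 20 becomes 0.79, 0.87, 0.93. With a visit-varying covariate, half of whose variance is person-level, the contrast is 0.67, 0.69, 0.72 at n = 15 and 0.81, 0.83, 0.85 at n = 20.

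**Step 5: covariates that respond to cannabis.** Section 9.1 predicts that heart rate and systolic pressure rise after cannabis. Assume no true effect, n = 15, r = 0.5, a covariate with half its variance person-level, between-person correlation 0.5 with the outcome, and no within-person slope. One-way contrast type I error is about 1% when the covariate does not differ between the two conditions, 6.7% when it differs by 1 SD and 20.7% at 2 SD. For between-person correlations of 0.3 to 0.7, the 1-SD range is 3.2% to 11.5%. A participant term returns it to about 5%.

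**Step 6: change scores.** If change from the same visit's baseline is analysed and all measurements are equally correlated, the person effect cancels. Type I error is 5.1% one-way and 5.0% with participant. Strain contrast power is 0.603 vs 0.598 (n = 15) and 0.723 vs 0.722 (n = 20).

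**Step 7: person-level covariates.** The variance of their slope is understated by a factor 1 + 4r, which is 3 at r = 0.5. A covariate with no effect is flagged 10%, 19%, 26% and 33% of the time at r = 0.1, 0.3, 0.5 and 0.7, instead of 5%.

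**The case against.** **The participant term may only be unstated.** Section 9.4.2 does say that the endpoints are repeated after each intervention, and nothing rules the term out. But the same section of the plan names repeated-measures methods for the secondary endpoints, so their absence here cannot be read as shorthand. If a participant term was intended, one sentence settles it.

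**The shortfall is modest at the planned size.** This largely stands. With 20 completers and r = 0.5, the one-way strain contrast is at 0.80 before covariates and 0.81 to 0.93 with them. The Phase II omnibus is 0.92. Only the Phase I strain omnibus (0.69) falls clearly short, and a strong person-level covariate could lift that too. A reader might infer that the trial is underpowered at its target; the figures do not support so broad a statement.

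**The outcome may be a change score.** Section 9.1 words the PWV hypothesis against resting baseline, and section 4.1 has measurements before and after consumption. On that reading the term gains almost nothing (step 6). The analysis sections do not say which outcome is used, so this limits the claim without removing it.

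**The inputs are stretched.** The correlation is not given. Pilot pre-post changes stand in for contrasts between conditions, the FMD pilot is an exercise response, and the pilot PWV falls although section 9.1 predicts a rise. The power values show size and are not forecasts.

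**Conclusion.** The point holds in conditional form. The model as written does not match the design, and its error term is wrong. The consequence depends on things the documents leave open:

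- **Post-consumption outcome, covariates unaffected by condition, positive residual correlation:** conservative tests and lost power, mainly in strain, with FMD borderline at 15 completers. At r = 0.1 the loss is small.
- **Heart rate or blood pressure covariates taken after consumption and shifted by cannabis:** type I error can exceed 5%, to about 7% and 21% in the cases shown.
- **Change scores with equal correlation:** little difference.
- **Person-level covariates such as fitness:** reported as influential too often wherever residual correlation is positive.

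A reader might infer that a one-way analysis of paired data always errs on the safe side and so cannot produce a false cannabis effect. The documents do not support that, because the timing of the haemodynamic covariates is not fixed and the plan itself expects heart rate and systolic pressure to respond.

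The direction of each effect is firm under its stated conditions. The sizes rest on an assumed r, with 0.5 used because it reproduces the stated 15. A change is needed before analysis: a participant term holds about 5% in every balanced case tested, for n − 1 error degrees of freedom.

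**What to change.** In Protocol sections 9.4.1 and 9.4.2 and the matching SAP sections:

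1. Replace the one-way ANCOVA with a repeated-measures ANCOVA or linear mixed model, with condition as a fixed effect and participant as a blocking effect (fixed or random).
2. Define the outcome as the post-consumption value, adjusted for the same visit's pre-consumption value where one is measured.
3. Use only pre-consumption haemodynamic covariates. With a random participant effect, split each covariate into its person mean and the deviation from it.
4. Analyse MSNA as a paired pre-post comparison.

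In Protocol section 9.2 and the SAP sample-size section, state the test, the assumed correlation and the resulting power. For a paired strain comparison at r = 0, 0.3, 0.5 and 0.7, power is 0.55, 0.68, 0.80 and 0.93 at n = 15, and 0.69, 0.82, 0.91 and 0.98 at n = 20.

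Reconcile sections 4.1 and 8.1 on echocardiography. The former has primary endpoints other than MSNA measured before and after consumption at each visit; the latter describes echocardiography before exercise at the control visit and after consumption at each study visit. Whether a pre-consumption covariate exists for strain depends on the answer.

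The cost is protocol and SAP wording. No participant or visit is added. The one possible exception is a pre-consumption echocardiogram, if the reconciled text turns out not to include one.

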## 9 STATISTICAL CONSIDERATIONS

### 9.1 STATISTICAL HYPOTHESES

- Primary Efficacy Endpoint(s):
  1. Pulse Wave Velocity will be increased following exercise, smoking high THC cannabis, and vaporizing high THC cannabis relative to resting baseline; effects of cannabis consumption and exercise are likely to be additive. Vaporizing high CBD cannabis will not increase pulse wave velocity.
  2. Percent flow mediated dilation will be decreased following exercise and smoking high THC cannabis; effects are likely to be additive. Vaporizing both high THC and high CBD cannabis will not decrease percent flow mediated dilation.
  3. Ejection fraction will be decreased following smoking and vaporizing high THC cannabis. Exercise and vaporization of high CBD cannabis will not be associated with reductions in ejection fraction.
  4. E/A Ratio will be decreased following high THC cannabis smoking only.
  5. Myocardial strain will be decreased following high THC cannabis smoking and vaporizing only.
  6. Myocardial twist will be decreased following high THC cannabis smoking and vaporizing only.
  7. Burst Frequency will be increased following high THC cannabis only.
  8. Burst Incidence will be increased following high THC cannabis only.

- Secondary Efficacy Endpoint(s):
  1. Systolic Blood Pressure will be increased following cannabis consumption and will be decreased following all bouts of exercise.
  2. Diastolic blood pressure will be unchanged under all conditions
  3. Heart rate will be increased following cannabis consumption and exercise.
  4. Stroke volume will be increased with exercise, and will be reduced following cannabis consumptions. These competing effects will result in an attenuation of increases in stroke volume when exercise is preceded by cannabis consumption.
  5. Cardiac output will be unchanged under all conditions
  6. Work completed will be reduced when preceded by cannabis consumption of all forms
  7. Average power output will be reduced when preceded by cannabis consumption of all forms
  8. Oxygen consumption will be reduced when exercise is preceded by consumption of high THC cannabis
  9. Rating of Perceived Exertion will be increased following consumption of high THC cannabis
  10. Rate-pressure product will be increased during exercise, when the bout is preceded by cannabis consumption.

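### The primary ANCOVA compares only active conditions and does not specify each endpoint's own pre-inhalation value, so it does not test the change in FMD and PWV from rest

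*Protocol*

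**What the plan says.** - **Measurement.** Protocol 4.1: "Primary endpoints will be examined pre- and post-consumption each visit", with nerve activity excepted. Protocol 8.1 says the same separately for arterial stiffness and for endothelial function.
- **Hypotheses.** Protocol 9.1 and SAP section 1 predict that PWV will increase after exercise and after smoked or vaporised THC, "relative to resting baseline; effects of cannabis consumption and exercise are likely to be additive". For FMD they predict a decrease after exercise and after smoked THC, without naming the reference.
- **Sample size.** Protocol 9.2 and SAP section 2: "15 participants are required to have a power of at least 0.8 with an alpha of 0.05". The supporting figures are all pre and post values. Protocol 9.4.1 adds: "All tests of significance will be two-tailed".
- **Primary model.** Protocol 9.4.1 and SAP 4.1 give a one-way ANCOVA with five levels per phase. In Phase I these are exercise alone, THC vaporised, THC smoked, and each of those two followed by exercise. Phase II replaces smoked THC with vaporised CBD.
- **Covariates.** Protocol 9.4.2 and SAP 4.2: "These covariates include heart rate, blood pressure, and pulse wave velocity". Section 9.4.1 adds fitness, resting heart rate and an open list of factors noticed during the study.

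**The concern.** The hypotheses concern movement away from rest, and so does the sample size. The model has no term that carries that comparison. None of its five levels is a resting, pre-inhalation state, and the outcome is not defined as a change. The value that would link each post measurement to its own resting level is not named as a covariate.

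Two things are at stake. A comparison among active conditions can be null even if PWV rose, or FMD fell, in all of them. And visit-to-visit variation in the resting value stays in the error term, although the trial already measures it.

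**Working it through.** **1. The plan's own figure.** Section 9.2 names neither a test nor a pre-post correlation. Assume a two-sided paired t-test with r = 0.5, so that SD_diff = sqrt(s1² + s2² − 2·r·s1·s2).

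| Endpoint | Pre (SD) | Post (SD) | Difference | SD_diff | Effect / SD_diff | n for 80% power |
|---|---|---|---|---|---|---|
| FMD, % | 4.8 (2.5) | 2.7 (1.7) | 2.1 | 2.211 | 0.950 | 11 |
| PWV, m/s | 7.4 (1.3) | 6.0 (1.3) | 1.4 | 1.300 | 1.077 | 9 |
| Strain, % | −18.3 (1.2) | −17.0 (1.9) | 1.3 | 1.664 | 0.781 | 15 (power 0.803) |

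The largest n is 15, which matches the plan. The match depends on r: strain needs 26, 20, 15 and 11 at r = 0, 0.3, 0.5 and 0.7. So 15 is consistent with sizing on pre-to-post change, but r is back-solved, and from strain rather than FMD or PWV.

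**2. What the planned model can show.** Suppose every condition moved PWV by the pilot size of 1.4 m/s. Each between-condition contrast would then be 1.4 − 1.4 = 0, and the model would show nothing. This holds whatever the correlation.

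**3. Precision.** The documents give no correlations, so these are assumed. Set the total variance of a measurement to 1, with a share s from the participant and v from the visit. The pre and post values at one visit share both, so their correlation is r = s + v. Values from different visits correlate s. Each participant completes every condition, so for n participants a contrast of post values has variance 2(1 − s)/n.

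- **(a) Within-person adjustment.** With a participant effect and the visit deviation of the pre-value as covariate, variance is multiplied by 1 − ρ², where ρ = v/(1 − s).
- **(b) Single pre-value added to the one-way model.** The slope is then about r, and the true contrast variance is multiplied by [(1 − s)(1 + r²) − 2rv]/(1 − s).

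| s, v | r | ρ | Cut under (a) | Ratio under (b) | Nominal residual cut r² |
|---|---|---|---|---|---|
| 0.4, 0.1 | 0.5 | 0.17 | 3% | 1.08 | 25% |
| 0.4, 0.2 | 0.6 | 0.33 | 11% | 0.96 | 36% |
| 0.3, 0.3 | 0.6 | 0.43 | 18% | 0.85 | 36% |
| 0.3, 0.2 | 0.5 | 0.29 | 8% | 0.96 | 25% |
| 0.5, 0.2 | 0.7 | 0.40 | 16% | 0.93 | 49% |
| 0.2, 0.3 | 0.5 | 0.38 | 14% | 0.88 | 25% |

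Worked example for s = 0.4, v = 0.1. Under (a), ρ = 0.1/0.6 = 0.167 and ρ² = 0.028. Under (b), (0.6 × 1.25 − 0.10)/0.6 = 0.65/0.6 = 1.08.

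**4. Change score instead of covariate.** With a participant effect, a plain change score multiplies contrast variance by 2(1 − ρ). At ρ = 0.40 that is 1.20, a loss. It gains only if ρ exceeds 0.5.

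**The case against.** **The five levels do carry some of the information.** Cannabis plus exercise against exercise alone estimates a cannabis effect during exercise. Cannabis plus exercise against cannabis alone estimates an exercise effect. That is true, but neither contrast compares cannabis at rest with no cannabis at rest. Without that fourth cell the additivity named in the hypotheses cannot be checked, and the pre-inhalation values are the data that could supply it.

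**PWV is on the covariate list, and the list is open.** A reader might infer that the plan ignores baseline PWV. The text does not support that: the listed PWV could mean the pre-inhalation value in the PWV model. The accurate statement is that the time point is not specified. For FMD no such reading exists. An open list of factors noticed during the study is not a pre-specified baseline adjustment.

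**Only the PWV hypothesis names resting baseline.** This stands. For FMD the reference is inferred from the predicted decrease and the pre/post pilot values.

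**A reader might claim a 25-49% precision gain.** That is r² at r = 0.5 to 0.7, the drop in nominal residual variance of a model that treats one participant's visits as independent. In this complete crossover the true ratio from adding one pre-value covariate to that model is 0.85 to 1.08, so it can even be slightly worse than no adjustment. The larger figure mostly reflects the missing participant term, which is a separate defect.

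**A reader might extend the point to heart rate, blood pressure and echocardiography.** The documents do not support this well. Heart rate and blood pressure are secondary endpoints with their own analysis (9.4.3), assessed after consumption (8.1). For echocardiography, 8.1 places the scan after consumption at cannabis visits, whereas 4.1 implies pre and post.

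**Conclusion.** The point holds for FMD and PWV. As specified, the primary analysis does not test change from rest, although hypothesis 1 states it, the FMD hypothesis implies it, and the sample size appears to be built on it. That conclusion rests on the wording alone. The endpoint's own same-visit pre-value is absent for FMD and unspecified in timing for PWV.

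The precision gain is secondary and modest: about 3-18% of contrast variance over a model with a participant effect, for assumed ρ of 0.17-0.43, and nothing if ρ is zero.

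It should not be inferred that no further information is needed for every level. Sections 4.1 and 8.1 define pre and post around cannabis consumption, and none is consumed at the exercise-control visit. The Schedule of Activities lists PWV and FMD at that visit without saying whether they precede exercise.

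**What to change.** In Protocol 9.4.2 and SAP 4.2, for FMD and PWV:

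1. Make the post value the outcome in a repeated-measures or mixed model with condition and a participant effect.
2. Include the same endpoint's same-visit pre-inhalation value as covariate, split into the participant's mean pre-value and the visit's deviation from it. Give the time point of every covariate, including PWV.
3. For hypotheses 1 and 2, report the post-minus-pre change within each condition with a 95% CI that respects the pairing. For the method or composition effect, report between-condition differences from the model.
4. State which pre-exercise FMD and PWV values serve as baseline at the exercise-control visit. If none is taken, limit the baseline-adjusted contrasts to the cannabis visits.
5. Leave the secondary heart rate and blood pressure analyses as they are. Defer echocardiography until 4.1 and 8.1 are reconciled on whether a pre-consumption scan is taken.

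The within-condition change answers the hypothesis as stated, but it has no untreated time control and should be reported with that caveat.

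The cost is SAP wording and one or two model degrees of freedom. The cannabis visits need no new measurements; the exercise-control visit needs its timing confirmed.
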